## **Background and Rationale**

*Clostridium difficile* is one of the most common causes of health care–associated infection. The incidence and severity of the CDI have increased alarmingly in many countries around the world since the outbreak of the hypervirulent strain NAP1 / BI / 027 at the beginning of the last decade. In Spain, it has also been a clear increase in incidence from 39 to 122 cases per 100,000 hospitalizations over 1999-2007 (1,2), despite the fact that the presence of the NAP1 / BI / 027 has been anecdotal until 2015. The higher incidence of CDI in Spain is related with the increment of antibiotic use, aging and more complex comorbidities of the hospitalized population (2). It is also likely that physicians' higher degree of suspicion and improved sensitivity of diagnostic tests had also contributed to magnify this rise.

In our country it has been shown that the use of antibiotics (in DDD) in the outpatient setting, especially fluoroquinolones and penicillin with beta-lactamase inhibitors (mainly amoxicillin-clavulanate) has increased significantly (3). Besides, the prevalence of fluoroquinolone use in hospital settings (patients receiving antibiotic per 100 hospitalized patients) has also risen significantly, going from 5.8 in 1999 to 10.2% in 2010 (4). In a recent study conducted in Canada, all antibiotics prescribed in hospital within 8 weeks of *C. difficile* infection (CDI) diagnosis were reviewed for appropriateness. More than 45% of antibiotic courses were deemed to be inappropriate because of incorrect diagnosis, inadequate or excessively broad spectrum of activity and prolonged duration of therapy (5). For this reason, programs of antibiotic stewardship have shown to

decrease the selective pressure that facilitates the emergence of multidrug resistant microorganisms and CDI. Development of hospital policies to limit the number and duration of antibiotic treatments has proved useful in reducing the incidence of CDI (6-9). In case of hospital outbreaks, programs improving antimicrobial use and strict cleaning measures and contact precautions are essential to control the spread of infection (10).

On the other hand, the risk of recurrence of CDI is high (between 20 and 30%). Patients with a first recurrence are at special risk of developing further episodes of recurrence, with the consequent inconveniences of that situation (repeated emergency department consults, numerous hospital admissions, negative effect on life quality, familiar disturbance...). Close monitoring of all patients with a CDI diagnosis may help to identify patients at particular risk of recurrence, in order to eliminate those potentially modifiable risk factors (11,12).

Early diagnosis and appropriate treatment of recurrent episodes, according to clinical practice guidelines (13), would improve patients' prognosis. Besides, monitoring by an infectious diseases physician who provided appropriate information to patients and families would ensure compliance with contact precautions and hygiene measures that would reduce the *C. difficile* dissemination. While prevention efforts have traditionally focused on the hospital setting, the recommendations should expand at community level (14). To sum up, CDI is a frequent nosocomial infection that often causes an increase in the average stay and medical expenses. Treatment, especially of successive recurrences, does not often conform to the guidelines for clinical practice. On the other hand, information that patients and families receive from physicians is usually poor. Specifically, it is unusual to provide information on measures to prevent the spread of infection once at home.

Evidence-based elements have been shown to reduce the incidence of multiple health-care associated and hospital acquired infections and, when bundled, led to even greater benefit than each of the strategies alone (15-19). Some studies have demonstrated a reduction in the incidence of CDI using a checklist of hospital interventions (20) or achieved the control of important outbreaks by means of a comprehensive "bundle" approach (21). A "bundle" for CDI should be based on interventions that have already shown to exert a high impact in reducing the risk of CDI (6, 22-25): prudent antibiotic prescribing, hand hygiene, environmental decontamination, isolation/cohort nursing and use of personal protective equipment. Apart from reducing the indiscriminate use of

antimicrobials, a stewardship program based on the detection and close monitoring of patients diagnosed with CDI, could offer personalized attention to this especially susceptible group of population, through systematic monographic medical visits and extended follow-up during the period of maximum risk of recurrence.

## Objectives

This study aims to evaluate the impact of an intervention, consisting on a bundle of measures.

### Primary objective:

- To reduce the recurrence rate of patients with a first episode of CDI hospitalized during the period of intervention by increasing the compliance with clinical practice guidelines (appropriate length and choice of drug for CDI specific treatment according to the severity of the initial episode) and by a close follow-up during the period of higher risk, avoiding factors that are known to predispose to recurrence.

### Secondary objectives:

- To reduce the rate of second and further recurrences by increasing the compliance with clinical practice guidelines (appropriate length and choice of drug for the treatment of first and further recurrences).
- To discontinue or to reduce the spectrum of unnecessary antibiotic treatments in this population ("antimicrobial stewardship"), especially during the episode of CDI and during the following 8 weeks.
- To discontinue inappropriate treatment of asymptomatic patients colonized by *Clostridium difficile*.
- To identify clinical and biological markers that could be used as predictors of recurrence.
- To identify patients with a high number of recurrences, that could benefit from novel or experimental treatments.

## Hypothesis

1. A bundle of measures specifically designed for patients with ICD and applied by and Infectious Diseases expert would improve the prognosis and reduce the risk of recurrence.
2. Some measures have proved to be effective to improve the prognosis of patients with a first episode of CDI. Probably the most relevant action is to stop the antibiotic treatment as soon as possible (grade of recommendation All according

to the IDSA guidelines), or at least to choose a low-risk antimicrobial treatment with minimum detrimental effect over the patient's microbiota. This measures cannot always be applied, but we hypothesize that an early assessment and monitoring by an Infectious Diseases expert would encourage attending physicians to evaluate the necessity of the inciting antimicrobial treatment and enable the decision of discontinue it, without substantial risk for the patient.

3. Although treatments shorter than 10 days of metronidazole have proved to increase the risk of recurrence and the recommendation is 10-14 days of metronidazole for a first mild or moderate episode of CDI (grade of recommendation AI), courses of 7 days are frequently prescribed. An initial assessment by an Infectious Diseases expert who makes a non-impositive recommendation would increase physicians' compliance with evidence-based recommendations.
4. Although oral vancomycin is the drug of choice for an initial episode of severe CDI (grade of recommendation BI) and vancomycin administered orally (and per rectum, if ileus is present) with or without intravenously administered metronidazole is the regimen of choice for the treatment of severe, complicated CDI, however, it is relatively frequent that the severity of the episode is not accurately assessed at diagnosis, which delays the start of appropriate therapy. An initial assessment by an Infectious Diseases expert who makes a non-impositive recommendation would increase physicians' compliance with evidence-based recommendations.
5. Although metronidazole should not be used beyond the first recurrence of CDI or for long-term chronic therapy because of potential for cumulative neurotoxicity, it is not uncommon that patients with multiple recurrences receive several courses of metronidazole. Patients with multiple recurrences would benefit from a close follow-up by an Infectious Diseases expert who appropriately diagnoses and treats every episode, following the evidence-based recommendations.

## **MATERIAL AND METHODS:**

**Study Design:** Exploratory, interventional before-after prospective, quasi-experimental study comparing the baseline phase (2015) with the interventional phase (2017)

## **Study Subjects:**

### Inclusion criteria:

- Patients diagnosed with a first episode of CDI in the University Hospital “12 de Octubre”, Madrid, Spain, requiring hospitalization or emergency room admission longer than 48 hours, from the beginning of the study on (1-February-2017).
- Patient or his/her representative sign the informed consent

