## **Patients selection and follow-up:**

The first 100 patients fulfilling the inclusion criteria will be included in the prospective phase of the study. Patients will be identified by means of daily report of the positive results from the Microbiology lab. They will be prospectively followed 8 weeks after the end of treatment for the episode of CDI. If there are one or more recurrences, the follow-up will endure until 8 weeks after the end of the last CDI treatment.

They will be retrospectively compared with patients diagnosed with a first episode of CDI during the previous year (2015) in which there was not a systematical intervention by a member of the Infectious Diseases Unit.

To ensure comparability, patients from the retrospective period will be chosen and matched with patients included in the prospective period according to the severity of the initial episode of CDI and to the Charlson Age-Comorbidity Index (CACI).

If patients diagnosed during 2015 are not enough to fulfil those comparison criteria, we will search backwards through patients diagnosed with a first episode of CDI during 2014 to be matched.

The retrospective follow-up will also endure until 8 weeks after the end of the last CDI treatment.

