**Leukocyte count to consider severity of the CDI:** Any white blood cell count (WBC) measured between two days before and two days following the date of the stool sample. If a patient had WBC measured on the date of the stool sample then this was selected. If they did not have WBC measured on the date of the stool sample but had WBC measured between one day before and one day following their stool sample, then this was selected. If they did not have WBC measured between one day before and one day following their stool sample but had WBC measured between two days before and two days following their stool sample, then this was selected. If they did not have WBC measured on the date of the stool sample but had WBC measured both one day before and one day following the date of stool sample, or had WBC measured both two days before and two days after the stool sample but not between these measurements, then the highest of the two measurements was selected.

**Definition of treatment response:** Treatment response is present when either stool frequency decreases or stool consistency improves and parameters of disease severity (clinical, laboratory, radiological) improve and no new signs of severe disease develop.

**Definition of recurrent CDI:** Recurrence is present when CDI re-occurs within 8 weeks of successfully completing treatment for CDI.

**Duration of diarrhea:** was the sum of days from day 1 to the last day with diarrhea, followed by 2 or more days without diarrhea.

**Antibiotics of high, medium and low risk for CDI:** according to the table proposed by Aldeyab et al (S3. J Antimicrob Chemother 2012; 67: 2988–2996).

**Table S3.** Risk classification of antibiotics

High risk	Medium risk	Low risk
Second-generation cephalosporins [J01DC; cefaclor, cefuroxime].	Combinations of penicillins including $\beta$ -lactamase inhibitors [J01CR; amoxicillin/clavulanic acid]	Combinations of penicillins including $\beta$ -lactamase inhibitors [J01CR; piperacillin/tazobactam] Penicillins with extended spectrum [J01CA; amoxicillin, ampicillin; pivmecillinam] $\beta$ -Lactamase-sensitive penicillins [J01CE; phenoxymethylpenicillin, benzylpenicillin]

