### **Data collection and analysis**

Patients in the pre-intervention period will be retrospectively identified from microbiological data. All isolates of *Clostridium difficile* from 2015 (and 2014, if necessary) will be revised backwards to choose comparable patients with those included in the prospective period, according to the severity of the first episode.

Data will be collected from electronic medical records which include daily medical evaluations and daily treatments administered to the patient.

Patients in the intervention period will be identified by daily reporting of positive tests for CDI from the Microbiology laboratory and prospectively followed by a member of the research team.

The variables will be collected in a coded database for further analysis.

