### **Statistical Plans**

We present an exploratory study which aim is to evaluate the impact of an intervention, consisting on a bundle of measures for patients diagnosed with a first episode of CDI. The bundle includes antimicrobial stewardship, close follow-up, optimization of specific treatment for CDI and potential search for clinical and biological markers of recurrence. The required sample size was estimated under the hypothesis that the application of a strategy based on a bundle to improve the management of CDI, would decrease the risk of recurrence as compared to the usual care performed in the retrospective period.

A recent review that evaluated the frequency of treatment failure and recurrence of CDI showed a recurrence rate after metronidazole treatment of 27.6% in studies performed in Europe during the previous 10 years.

Based in the previous literature, we expected a cumulative incidence of recurrence in the control group of 27.6%. The study would require a sample size of 99 for each group (i.e. a total sample size of 198, assuming equal group sizes), to achieve a power of 80% for detecting a reduction in proportions of 0.15 between the two groups (reference group - intervention) at a two sided p-value of 0.05.

1. Vardakas KZ, Polyzos KA, Patouni K, Rafailidis PI, Samonis G, Falagas ME. Treatment failure and recurrence of *Clostridium difficile* infection following

treatment with vancomycin or metronidazole: a systematic review of the evidence. *Int J Antimicrob Agents* 2012; 40:1–8.

2. Ralph B. D'Agostino, Sr, Sylva H. Collins, Karol M. Pencina, Yin Kean, and Sherwood Gorbach. Risk Estimation for Recurrent *Clostridium difficile* Infection Based on Clinical Factors. *Clinical Infectious Diseases* 2014 58: 1386-1393.

The data of qualitative variables will be expressed as absolute values and relative frequencies. The data of quantitative variables will be shown as mean  $\pm$  standard deviation should be demonstrated normal distribution or median with interquartile range otherwise. Categorical variables will be compared using  $\chi^2$  or Fisher's exact test for paired samples. Continuous variables will be compared using the Student's t-test or the Mann-Whitney U test for paired samples.

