### **ETHICAL ASPECTS:**

Before the beginning of the study, this protocol will be submitted for consideration by the Spanish Agency for Medicines and Health Products ("AEMPS") for classification and by the Ethics Committee for Clinical Research (EC) of the University Hospital 12 de Octubre, to obtain the approval.

Since no active intervention on the pre-intervention group will be performed, the data will be collected in a database to which only research team have access and all information related to the study will be strictly confidential and treated according to the Organic Law

15/1999 on Protection of Personal Data, and Law 14/2007 of Biomedical Research, Ethics Committee will be asked to accept the study without the necessity of informed consent for this group.

Informed consent for the patients included in the study during the period of intervention will be requested.

The entire study will be conducted in accordance with the principles of the revision of Seoul, Korea (October 2008) of the Declaration of Helsinki for research in humans. Copies of the Declaration of Helsinki and its subsequent amendments will be provided upon specific request or can be downloaded from the website of the World Medical Association in [http://www.wma.net/e/policy/b3 .htm](http://www.wma.net/e/policy/b3.htm).

The study will be conducted according to the protocol, which ensures compliance with the rules of Good Clinical Practice (GCP), as described in harmonised tripartite guidelines on Good Clinical Practice of 1996.

According to the guidelines of the SAS / 3470/2009 Order on post-authorization observational studies, such projects must be reviewed by an independent committee (except in certain specific cases). For these reasons, this study was sent to a clinical research ethics committee for evaluation and timely notification to the Spanish Agency for Medicines and Health Products (AEMPS) for classification will be sent.

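### Signed consent is an entry condition only in the intervention period, so patients who die, leave or refuse before signing are missing from one group but can be chosen as matched controls in the other

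*Combined protocol and SAP*

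**What the plan says.** For the intervention period, Inclusion criteria lists a first episode of CDI from 1 February 2017 and adds: "Patient or his/her representative sign the informed consent". Ethical Aspects agrees: "Informed consent for the patients included in the study during the period of intervention will be requested". Patients selection and follow-up then fixes the group: "The first 100 patients fulfilling the inclusion criteria will be included in the prospective phase of the study". Candidates come from a daily laboratory report. No time limit for obtaining the signature is given.

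For the control period, Data collection and analysis says: "Patients in the pre-intervention period will be retrospectively identified from microbiological data". Ethical Aspects says: "Ethics Committee will be asked to accept the study without the necessity of informed consent for this group". Controls are matched "according to the severity of the initial episode of CDI and to the Charlson Age-Comorbidity Index (CACI"), and 2014 is available if 2015 does not yield enough matches.

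On the outcome, Definitions says: "Recurrence is present when CDI re-occurs within 8 weeks of successfully completing treatment for CDI". Statistical Plans says "we expected a cumulative incidence of recurrence in the control group of 27.6"%, with a planned reduction of 15 points. No section states which patients form the denominator of the recurrence rate, or how a patient who dies before recurring is counted.

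**The concern.** The two groups enter the study at different points in the illness. An intervention patient has to have a positive report, be approached, and sign or have a representative sign. Anyone lost on the way is replaced by the next eligible patient and leaves no trace in the data. A control has to have only a positive report and a suitable severity and comorbidity score.

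The plan relies on matching for comparability, but both matching factors are baseline measures. They do not condition on surviving, staying in hospital or agreeing to take part. The adjusted conditional logistic model cannot recover a selection step that nobody recorded.

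Two kinds of bias can follow in the primary comparison:

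- **Early death.** A control who dies within days cannot recur. If counted in the denominator, that patient lowers the control rate and hides part of any benefit.
- **Refusal.** If patients who refuse have a different recurrence risk from those who consent, the intervention group is a selected sample and the controls are not. The sign depends on which way the risk differs.

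**Working it through.** **Inputs from the documents.** Control recurrence 27.6%; planned reduction 15 points, so intervention rate 27.6 − 15.0 = 12.6%; two-sided 0.05; 99 per group for 80% power (Statistical Plans); 100 intervention patients to be enrolled (Patients selection and follow-up).

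**The plan's own figure.** The usual pooled formula for two independent proportions, with mean p̄ = (0.276 + 0.126)/2 = 0.201, gives

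n = [1.96·√(2·0.201·0.799) + 0.842·√(0.276·0.724 + 0.126·0.874)]² / 0.15² = 110.9, so 111 per group.

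The stated 99 is not reproduced. Power is 75.4% at 99 and 75.8% at 100. That is a separate matter; here it only sets 75.8% as the starting value.

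**Early deaths.** Let m be the share of controls who die between their positive report and the day on which an equivalent intervention patient would have signed. Suppose they all stay in the denominator as non-recurrences, that no such deaths occur in the intervention group, and that 27.6% is the rate among those who survive to that day. Then

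observed control rate = 0.276 × (1 − m); shift = 0.276 × m.

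Power at 100 per group is Φ[(d − 1.96·s₀)/s₁], where d is the observed difference, s₀ = √(2p̄(1 − p̄)/100) and s₁ = √((p₁(1 − p₁) + p₂(1 − p₂))/100). For m = 0.10, p₁ = 0.2484, p₂ = 0.126, d = 0.1224, s₀ = 0.0552 and s₁ = 0.0545. The argument is 0.262, so power is 60.3%.

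| m (assumed) | Control rate | Shift, points | Difference from 12.6%, points | Power |
|---|---|---|---|---|
| 0 | 27.6% | 0 | 15.0 | 75.8% |
| 1% | 27.3% | 0.3 | 14.7 | 74.4% |
| 2% | 27.0% | 0.6 | 14.4 | 73.0% |
| 3% | 26.8% | 0.8 | 14.2 | 71.5% |
| 5% | 26.2% | 1.4 | 13.6 | 68.5% |
| 10% | 24.8% | 2.8 | 12.2 | 60.3% |

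With no true effect, the shift column is also the amount by which the bundle would look worse than usual care.

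**The same deaths under the other denominator.** If the rate is taken only among patients who successfully completed treatment, someone who dies before completion is in neither numerator nor denominator, in either group. The shift from early deaths is then close to zero.

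**Refusals.** Let f be the share refusing and r their recurrence risk relative to consenters. With no true effect and an overall rate of 27.6%, the consenters' rate is 0.276/[(1 − f) + f·r]. Both f and r are assumptions, and the following only shows that the sign is open. At f = 0.3 and r = 0.5 the consenters' rate is 32.5%, and the bundle looks 4.9 points worse. At f = 0.3 and r = 2 it is 21.2%, and the bundle looks 6.4 points better.

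**The case against.** The strongest objection concerns the early deaths. Recurrence is defined only after treatment has been successfully completed, and follow-up runs to 8 weeks after the last treatment ends. It is natural to read this as an analysis of treatment completers, in which early deaths fall out of both groups. A reader might infer from the consent rule that early deaths will be counted as control non-recurrences. The documents do not say so: the definition fixes the event and leaves the denominator open. The early-death bias is therefore conditional.

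Second, the interval that matters may be only days, since patients are found by daily report and a representative may sign. A share of 1–3% is as compatible with the documents as a larger one. It is tempting to assume that one control in five dies in this interval, which would give a control rate of 22.1% and power of 42.4%. Nothing in the documents supports a share of that size.

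Third, severity and age-comorbidity are plausible predictors of early death, so matching may remove part of the imbalance. The calculation gives no credit for this and treats the groups as independent, although the plan specifies conditional logistic regression. Its results are approximate.

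Fourth, the study is exploratory, and consent only in the prospective period is common in before-after designs. That explains the asymmetry but does not remove it. The plan still makes a powered two-sided comparison between the groups.

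What stands after these points is the unequal entry rule, the absence of an equivalent entry point for controls, and the absence of a record of who was lost before consent. Consent by a representative helps with incapacity, but not with death, departure or refusal.

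**Conclusion.** The concern holds as a conditional bias of modest or unknown size. The unequal entry rule is explicit, and no section compensates for it. If early deaths remain in the control denominator as non-recurrences, an assumed 1–10% share biases the comparison against the bundle by 0.3–2.8 points. If only treatment completers are analysed, this part largely disappears. The plan does not say which applies.

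Selection by refusal remains under either denominator. Its size cannot be derived from the documents and it can act in either direction. A reader might infer that the asymmetry as a whole works against the bundle, or as a whole favours it. Neither follows, because the two mechanisms can oppose each other and neither share is known. The consent waiver is described as something to be requested, but control selection from records is planned on that basis.

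**What to change.** In Patients selection and follow-up, and in Data collection and analysis:

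1. Record the days from positive stool report to signed consent for each intervention patient. Accept a candidate control as that patient's match only if he or she was alive and still under care the same number of days after his or her own positive report. A further condition that the control be free of recurrence on that day would add almost nothing, because recurrence by definition follows completed treatment.
2. State one recurrence denominator and apply it to both groups, including how deaths are counted.
3. From the existing daily laboratory report, log intervention-period patients who met every other criterion but died, left or refused before consent, and report the number in each category. Start the log with enrolment.

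The first change gives both groups an equivalent entry point with respect to early death and departure. It cannot identify which earlier patients would have refused; the log makes that loss visible without correcting it.

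The cost is one more chart-selection rule, a short log, and a few candidate controls lost, which the 2014 backfill can cover.
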